The overall aim of the FREE Study is to inform valid, representative and cost-effective future use of the FS-ICU questionnaire into quality improvement programmes for adult critical care services in the NHS in the UK.

The objectives of the FREE Study are:

- to test the face and content validity and the comprehensibility of the FS-ICU;
- to establish the internal consistency, construct validity and reliability of the FS-ICU;
- to describe family satisfaction using the FS-ICU and explore how family satisfaction, measured with the FS-ICU, varies by:
 - family member;
 - patient characteristics;
 - unit/hospital characteristics;
 - other contextual factors; and
 - country (through comparison with FS-ICU data held in Canada);
- to model approaches to sampling to achieve representative sampling for feasible, cost effective future use of the FS-ICU in quality improvement in the NHS.

4. Study design

The FREE Study is a mixed methods study comprising a psychometric evaluation (FREE-Qual) leading to a multicentre cohort study.

The objectives of the FREE Study will be addressed in two sub-studies.

FREE-Qual

FREE-Qual is a qualitative study (see: Section 5) which will address the first objective by testing the face and content validity and the comprehensibility of the validated Canadian FS-ICU. Modifications to the FS-ICU questionnaire will then be made, if required.

The FREE Study

FREE is a multicentre cohort study (see: Section 6) which will address the remaining objectives using the UK adaptation of the FS-ICU questionnaire (FREE-Qual).

Staff at twenty adult, general critical care units will identify up to four family members for consecutive patients admitted to their unit who stay more than 24 hours. Family members who consent to take part will be sent a questionnaire three weeks following patient discharge from the critical care unit.

The recruitment period will be one year, chosen to avoid bias from seasonal variation in case mix and workload. A psychometric assessment of the FS-ICU will be undertaken using data collected during the first month.

5. FREE-Qual

Research Ethics Committee reference:	12/YH/0415
Sponsor reference:	ICNARC/02/05/12
NIHR CRN Portfolio ID number:	112459
Protocol version:	1.0
Protocol version date:	31 July 2012

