7.1 Sample size and recruitment rate calculation

The duration of recruitment will be one year, chosen to avoid bias from seasonal variation in case mix and workload. Data from the CMP database indicates that an average of 520 patients are admitted per unit, per year, and of these, 74% stay at least 24 hours, corresponding to 7,700 patients (approximately 19,250 family members). Assuming an average of 2.5 family members per patient and a 66% response rate,¹⁵ a total sample of approximately 12,700 responses, associated with 6,700 patients will be achieved. Using available FS-ICU data, published and unpublished, we anticipate mean baseline satisfaction domain scores of 80 with standard deviation 20. This sample size will give >90% power to detect ($p<0.01$) a binary patient factor present in 10% of the patient population associated with an increase or decrease in domain score of 4 points.

The sample size estimate was updated following completion of the first full quarter of recruitment, based on the CMP data submitted for that quarter from the actual participating sites and FREE Study data collected. Revised targets were calculated for each site based on successful recruitment of an average of 2 family members for 80% of patients staying at least 36 hours¹ in the critical care unit, allowing that on average 10% of patients may have no family members visit. Based on these revised targets, we anticipate recruitment of 14,200 family members (of 7,100 patients). Assuming a 60% response rate, a total sample of approximately 8,500 responses associated with 5,500 patients will be achieved. This sample size retains >90% power to detect ($p<0.01$) a binary patient factor present in 10% of the patient population associated with an increase or decrease in domain score of 4 points.

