A number of potential alternative sampling frames will be constructed based on results of the regression models, and varying the numbers of patients sampled and the timing(s) of the samples within the year. Potential sampling frames include: 100% sampling over a short timeframe; simple random sampling; and random sampling stratified by patient/admission characteristics (e.g. age, sex, survival status, length of stay). The representativeness of the proposed sampling frames will be assessed by assessing the correlation between the FS-ICU domain scores calculated in the sample and in the total population for each critical care unit. Uncertainty in the correlation will be assessed using bootstrapping techniques.

8. Ethical compliance

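### The correlation chosen to judge sampling frames does not register bias common to all units, and its values are not comparable between frames of different size

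*Protocol*

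**What the plan says.** One objective in section 3 is "to model approaches to sampling to achieve representative sampling" for feasible and cost-effective future use of the questionnaire. The last paragraph of section 7.2 sets out the method. Alternative frames are to be built from the regression results, "varying the numbers of patients sampled and the timing(s) of the samples within the year". The candidates are listed: "Potential sampling frames include: 100% sampling over a short timeframe; simple random sampling; and random sampling stratified by patient/admission characteristics". Representativeness is then assessed by "assessing the correlation between the FS-ICU domain scores calculated in the sample and in the total population for each critical care unit". The only addition is this: "Uncertainty in the correlation will be assessed using bootstrapping techniques".

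No signed difference, RMSE, limits of agreement, comparison at equal size or check of patient mix is stated. Sections 4 and 7.1 give avoidance of seasonal bias as the reason for recruiting over a full year.

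**The concern.** A representative frame should give a unit about the score that the full year's data would give. The correlation measures something narrower: whether units that are high in the full data are also high in the sample. If a frame moves every unit up or down together, or stretches or shrinks the differences between units by a common factor, the correlation stays the same.

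Such bias is plausible for the listed frames. A census over a short period may catch a seasonal shift affecting all units, which the protocol itself treats as a source of bias. A stratum over-sampled alike everywhere and not weighted back would act in the same way.

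The sample is also drawn from the total it is compared with. The two share data, and the share grows with the sampling fraction, which the plan deliberately varies between frames.

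At stake is the recommendation on how the NHS should sample families. A high correlation could be offered in support of a frame whose scores are at the wrong level.

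**Working it through.** **Inputs from the protocol.** Section 4: "Staff at twenty adult, general critical care units", so 20 points in the correlation. Section 7.1: "a total sample of approximately 8,500 responses associated with 5,500 patients will be achieved", so 8,500/20 = 425 responses per unit. Section 7.1: "mean baseline satisfaction domain scores of 80 with standard deviation 20". The same section takes 4 points as the difference to be detected; I use it only as a yardstick for bias.

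**Assumptions.** The between-unit SD (τ) is not given, so I use 0 to 5 points. The sampling fraction (f) is not fixed, so I use 1/12 to 50%. Responses are treated as independent within a unit. With 8,500/5,500 = 1.55 responses per patient, similarity between relatives would add some sampling noise but would not alter the invariance.

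**The plan's own figure.** The protocol gives no figure for this correlation. Its power statement (over 90%, two-sided 0.01 assumed, factor in 10% of patients) reproduces. For N = 5,500, SE = 20·√(1/550 + 1/4,950) = 0.899, 4/0.899 − 2.576 = 1.87, and power is 97.0%. For N = 8,500 it is 99.8%. That figure is not in dispute.

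**Step 1: overlap.** Under simple random sampling within units of size n = 425 with SD s = 20,

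r = √[(τ² + s²/n) / (τ² + s²/(fn))].

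At τ = 0 this is √f. At τ = 3 and f = 0.25 it is √[(9 + 0.941)/(9 + 3.765)] = 0.88. A sample independent of the total would give τ²/√[(τ² + s²/n)(τ² + s²/(fn))].

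| f | τ = 0 | τ = 0, independent | τ = 3 | τ = 3, independent |
|---|---|---|---|---|
| 1/12 | 0.29 | 0 | 0.70 | 0.63 |
| 10% | 0.32 | 0 | 0.74 | 0.67 |
| 25% | 0.50 | 0 | 0.88 | 0.80 |
| 50% | 0.71 | 0 | 0.96 | 0.87 |

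**Step 2: bias.** Simulation with 20 units, τ = 3 and 3,000 replicates; mean values:

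| Frame | r | Signed difference | RMSE | Concordance |
|---|---|---|---|---|
| 25%, unbiased | 0.877 | 0.0 | 1.66 | 0.86 |
| 25%, every unit 4 points low | 0.874 | −4.0 | 4.31 | 0.49 |
| 25%, spread of unit scores halved | 0.875 | 0.0 | 1.76 | 0.74 |
| 25%, bias differing between units, SD 2 | 0.763 | 0.0 | 2.57 | 0.72 |
| 25%, bias differing between units, SD 4 | 0.580 | 0.0 | 4.29 | 0.49 |
| 10%, unbiased | 0.726 | 0.0 | 2.88 | 0.68 |
| 1/12 (a month's worth), unbiased | 0.688 | 0.0 | 3.22 | 0.63 |
| 1/12, every unit 4 points low | 0.685 | −4.0 | 5.11 | 0.40 |

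The 4-point result does not depend on τ: at f = 25% the correlation without and with the shift is 0.789 and 0.790 at τ = 2, and 0.947 and 0.948 at τ = 5. As a check, RMSE should be 20·√[(1 − f)/(425f)] = 1.68 without bias and √(1.68² + 4²) = 4.34 with it; the simulation agrees.

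Bias differing between units (SD 2, 25% sample) gives 0.76, close to the 0.73 of an unbiased 10% sample. The correlation alone does not say which of the two has occurred.

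**The case against.** A reader might infer that the correlation cannot detect any bias. It can: bias that differs between units takes it from 0.88 to 0.76 or 0.58. That is the kind of bias that distorts comparisons between units, and section 2 raises sampling in the context of comparing providers. If every unit uses the same frame, a common shift leaves relative positions intact. The correlation therefore measures a relevant property, and this stands. It is not the whole of representativeness, however: units also receive their own reports (section 13.2), and scores are compared with Canadian data (section 7.2). Both uses need the right level.

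A reader might also infer that the largest frame must win. No rule says that the highest correlation is chosen, and the objective weighs feasibility and cost. Part of the rise with f is legitimate, since a larger sample estimates the full-year score better. RMSE improves with f too: 2.9, 1.7 and 1.0 points at 10%, 25% and 50%. What remains is that values from frames of unequal size cannot be set side by side as evidence of representativeness.

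Imprecision from having only 20 units is not a separate flaw. At τ = 3 and f = 25%, 95% of simulated correlations lie between 0.74 and 0.96, but the planned bootstrap addresses this. It describes uncertainty in the correlation and does not make it sensitive to a common shift.

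The size of any bias is not in the documents. Simple random sampling is unbiased by design, and stratified sampling is unbiased if proportionate or weighted; the protocol specifies neither. With the protocol's reference factor (4 points, 10% of patients), raising that group to half of an unweighted sample would shift the mean by 4 × (0.50 − 0.10) = 1.6 points. Month of the year is already a predictor in the models that inform the frames. The 4-point shift is thus an illustration, not a forecast.

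Finally, the coefficient is not named, and an absolute-agreement version would register a shift. An unseen analysis plan may add summaries, but the protocol as written says correlation, and the ordinary reading is the product-moment coefficient.

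**Conclusion.** The concern holds in limited form. The one criterion that the protocol states for representativeness does not register a shift or rescaling common to all units, does not separate unit-varying bias from sampling noise, and has a baseline of about √f from overlap alone. With τ = 3 and a 25% sample, r is about 0.88 with or without a 4-point shift, while RMSE goes from about 1.7 to 4.3.

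The insensitivity to a common shift or rescaling is a property of the product-moment coefficient and needs no assumption about τ. The sizes rest on the assumed τ, f and shift, and on independent responses. The documents do not support saying that all bias goes undetected, that larger frames win automatically, or that a biased frame will be recommended. Severity: should-fix. The step is exploratory, follows data collection, and leaves the regression estimates untouched.

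**What to change.** Amend the last paragraph of section 7.2 as follows.

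- For each frame and sample size, make the mean signed difference between sample and full-year unit scores, and the RMSE or limits of agreement, the main criteria.
- Report the share of units whose funnel-plot classification changes. This matters for rescaling: when the spread is halved, the signed difference stays at 0 and RMSE moves only from 1.66 to 1.76. A concordance coefficient (0.86 to 0.74) would help here too.
- Compare frames at equal numbers sampled, or against the held-out remainder, since RMSE also falls with sample size. Set the results against the number of questionnaires mailed.
- Resample patients within units, keeping relatives of the same patient together.
- Keep the correlation as a secondary measure of how well relative unit positions are preserved.

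The cost is a few lines of text and slightly more analysis from resampling already planned. No new data are needed.

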8.1 Central ethical compliance

The FREE Study will be conducted in accordance with the approved Study Protocol, ICH GCP guidelines, the Data Protection Act 1998, the Medical Research Council's (MRC) Guidelines for Good Clinical Practice in Clinical Trials and Good Research Practice: Principles and guidelines (which are based on the principles of ICH GCP), as well as the ICNARC CTU's research policies and procedures.

8.1.1 FREE-Qual

The study will be conducted in accordance with the ethical principles founded in the Declaration of Helsinki. As family members are being recruited through the NHS, because of their relationship to NHS patients, favourable ethical opinion from an NHS REC as well as full R&D approval will be required before starting this study.

It is anticipated that the key ethical considerations with this study will be around ensuring that the cognitive interviews with the family members are conducted sensitively and respectfully. The family members may well be stressed and worried at the time they are approached by the research nurses. At the time of interview, three weeks after their family member was discharged from ICU, they will have recently gone through a stressful and emotional event and may still have significant caring responsibilities. The critical care research nurses are experienced in approaching families for consent for studies, and have undergone further training in the consent process organised by Northumberland Tyne and Wear CLRN. The Research Associate will also be experienced and skilled in communication with members of the public. In addition, before the family members are contacted by the Research Associate, the research nurses will check the electronic patient record

system of Newcastle upon Tyne Hospitals NHS Foundation Trust to see that their loved one has not died/been readmitted elsewhere after discharge from the ICU. This is to limit the chance of an approach to interview in those cases, if at all possible.

A second consideration is the risk that family members may feel like they themselves, rather than the questionnaire, are been tested, and may feel embarrassed or under pressure if they don't understand the wording of a question. Family members will be reassured that they are not being assessed personally, but rather the aim is to find out whether the questionnaire is understandable and acceptable to people like them.

Otherwise, it is anticipated that the ethical issues are likely to be minimal.

It is important to note that the patients in ICU are not the subjects of the research, they play no role in the FREE-Qual study, except that the fact that they are in ICU for more than 24 hours is a requirement for enrolling their family members into the study.

8.1.2 FREE Study

A favourable opinion will be obtained from the appropriate Research Ethics Committee (REC) and Local Research & Development (R&D) approval will be obtained prior to commencement of the study at all sites.

The ICNARC CTU will submit annual progress reports to the REC. Amendments to the Study Protocol will be submitted in writing to the REC for approval.

The FREE Study is nested in the CMP, the national comparative audit of patient outcome from critical care, which will enable investigation into whether or not family satisfaction varies by patient characteristics, such as severity of illness. Support for the collection and use of patient identifiable data has been approved for the CMP by the National Information Governance Board for Health and Social Care (NIGB) under Section 251 of the NHS Act 2006 (originally enacted under Section 60 of the Health and Social Care Act 2001) – Approval Number: PIAG 2-10(f)/2005.

8.2 Local ethical compliance

It is the responsibility of the PI to obtain the necessary local approvals for the FREE Study, including approval from the NHS Hospital Trust Research & Development (R&D) department. Evidence of local NHS Hospital Trust R&D approval must be provided to the ICNARC CTU prior to the unit commencing recruitment.

The FREE Study will only be conducted at units where all necessary local approvals for the study have been obtained and a Research Agreement between the NHS Hospital Trust (unit) and the ICNARC CTU has been signed.

8.3 Confidentiality and data protection

Family members who agree to participate in the study will be asked to provide their full name and postal address to enable the ICNARC CTU to post the FS-ICU questionnaire to them. This information will be entered and stored securely on a secure web-based data entry system. The ICNARC CTU will act to preserve participant confidentiality and will not disclose or reproduce any information by which participants could be identified.

ICNARC is registered under the Data Protection Act 1998 and all ICNARC CTU staff undergo data protection and ICH GCP training.

9. Study closure

9.1 End of study

The “end of the study” will be when the last family member has completed the FS-ICU questionnaire, at which point the ‘declaration of end of study’ form will be submitted to the REC by the ICNARC CTU.

9.2 Archiving study data

At the end of the study, the ICNARC CTU will archive securely all centrally-held study-related documents and electronic data for a minimum of ten years in accordance with the ICNARC CTU Standard Operating Procedure (SOP) on archiving trial/study data based on ICH GCP guidelines. After 10 years, arrangements for confidential destruction of all documents and data will then be made.

It is the responsibility of local PIs to archive all locally-held study-related and essential documents at the hospital for a minimum of ten years after the end of the study. Essential documents are those which enable both the conduct of the study and the quality of the data produced to be evaluated and to show whether the unit complied with the principles of ICH GCP and other applicable regulatory requirements.

The ICNARC CTU will notify PIs when study documents should be archived and will provide guidance on archiving procedures in the study-specific SOP.

All archived documents, held centrally and locally, should be available for inspection by appropriate authorities upon request.

10. Study management

10.1 Good research practice

The FREE Study will be managed according to the MRC’s Guidelines for Good Clinical Practice in Clinical Trials and Good Research Practice: Principles and guidelines, which are based on the principles of ICH GCP. The ICNARC CTU has developed its own policies and procedures, based on these MRC guidelines, for the conduct of all its research activities. In addition, ICNARC has contractual confidentiality agreements with all members of staff. Policies regarding alleged scientific misconduct and breach of confidentiality are reinforced by disciplinary procedures.

10.2 Study Management Group

All day-to-day management of the FREE Study will be the responsibility of the Study Management Group (SMG). Members of the SMG include the FREE Study Coordinator, the Chief Investigators ([name] and [name]) and the co-investigators. The SMG will meet regularly to discuss management and review progress of the study against timelines/milestones.

10.3 Study Steering Committee

The FREE Study will be supervised by the Study Steering Committee, which will be chaired by an independent member, [name], Consultant Nurse, Adult Critical Care Unit, St. Thomas' Hospital.

10.4 Role of the ICNARC Clinical Trials Unit

The ICNARC CTU will be responsible for the day-to-day management of the study and will provide study-specific SOPs for all aspects of the study. ICNARC will act as custodian of the data.

11. Sponsorship and Indemnity

ICNARC is the sponsor for the FREE Study and holds professional indemnity insurance (Markel International Insurance Co Ltd) to meet the potential legal liability of the sponsor and employees for harm to participants arising from the design and management of the research.

Indemnity to meet the potential legal liability of investigators/collaborators for harm to participants arising from the conduct of the research is provided by the NHS indemnity scheme or through professional indemnity.

12. Funding

The FREE Study is funded by the NIHR Health Services & Delivery Research (HS&DR) Programme (Project No. 11/2003/56).

13. Dissemination policy

13.1 Progress of study

To ensure all stakeholders are kept aware and informed, ongoing progress of the FREE Study will be disseminated to: participating units through newsletters, emails and telephone; to the wider critical care community through relevant professional newsletters, professional meetings and national and international conferences; and to consumers via the ICNARC and ICUsteps websites.

13.2 Study results

The results of the FREE Study will be widely and actively disseminated.

Staff from participating units will be invited to a Collaborators' Meeting at which the results of the FREE Study will be presented. All participating units will receive individual, comparative reports on family satisfaction. Variation in family satisfaction across critical care units will be summarised by presenting the domain scores for each unit, anonymised, in the form of funnel plots, both before

and after adjustment for family member, patient and unit/hospital characteristics. Feedback will be elicited from critical care unit staff attending the Collaborators' Meeting on the best mode of presentation with a view to maximizing the potential for using the results to improve quality.

ICNARC has access to both patients and their families and close friends from its recent support and collaboration in three modules (http://www.healthtalkonline.org/Intensive_care/) for the award winning website healthtalkonline (<http://www.healthtalkonline.org/>) and through its work with ICUsteps, the intensive care patient support charity, on the FREE Study. ICNARC has established strong links with the critical care community, which includes: a large network of NHS critical care units (>200) in the UK through its National Audit Programme and CTU; close links with the Intensive Care Society (ICS), the representative body in the UK for critical care professionals (ICNARC has representation on the ICS Council and membership of the ICS Research Committee); close links with the British Association of Critical Care Nurses (BACCN) and the Royal College of Nursing Critical Care and In-flight Nursing Forum (RCN CCINF); representation on the NIHR Comprehensive Clinical Research Network Critical Care Specialty Group.

The final report to the NIHR HS&DR Programme will present a detailed description of the FREE Study and the results along with recommendations for future policy and practice and future research. The results of the FREE Study will be presented at: regional critical care network meetings; national professional conferences (e.g. ICS, BACCN, RCN CCINF); the Annual Meeting of the ICNARC Case Mix Programme; the Annual Meeting of the UK Critical Care Research Forum; and at national and international critical care conferences/meetings.

References

1. Department of Health. *Equity and excellence: Liberating the NHS*. London: The Stationery Office Limited, 2010.
